We require a minimum of 299 women in postpartum observation period in each arm to detect an increase of at least 10% contraceptive prevalence rate (CPR) in the intervention arm, compared to the women in the control arm (20% vs 10% in the intervention and control arm, respectively) with $deff=1.5$ at 80% statistical power. Assuming about 20% lost-to-follow-up and non-response rate, we target to enroll 375 women in each arm. We consider that it will be sufficient to select 1 PHCU and its attached *kebeles* in each of the two *woredas* to ensure adequate sample size, with 2 PHCU randomly assigned to the intervention area (1 per *woreda*) and 2 to the control area (1 per *woreda*). The eligible women in 3rd trimester who consent to participate in the study voluntarily will be recruited and be interviewed at enrollment and at 12-month PP.

We used $p_1=0.2$ (20% PP contraceptive uptake by the final round of observation in the intervention arm) and $p_2=0.1$ (10% in the comparison arm). We considered $deff=(1+[m-1]\rho)= 1.5$. Because we are targeting 375 sample size of pregnant women in each arm consisting of 2 PHCUs, this implies $m=188$ AND $\rho=0.0027$.

Because the selected PHCUs are adjoining *woredas* of the same zone, it is expected that they will be quite similar, and in addition, the underlying population are all similar in terms of postpartum status; hence ρ very small (the larger the heterogeneity, the larger the ρ value). The Ethiopia DHS 2011 results suggest that the $deff$ of contraceptive use in all 11 regions are much smaller than the national level $deff$ of CPR (Appendix B – Estimates of Sampling Errors); *woreda* level $deff$ is expected to be much smaller due to less heterogeneity at *woreda* level, compared to the region/state level. In all regions, method specific $deff$ was <1.5 . So, we considered that of $deff=1.5$ is applied in this study is reasonable and practical. A study on postpartum use of contraceptive method at a *woreda* level in Ethiopia also had $deff=1.5$ (Abera Y, Mengesha ZB, Tessema GA. Postpartum contraceptive use in Gondar town, Northwest Ethiopia: a community based cross-sectional study. BMC Women's Health. 2015;15:19.)

Sample size requirements are included below based on the average number of providers and HDAs and managers in each *kebele*. See Table 4: Sample Size Summary

Table 4: Sample Size Summary

Study Participant	Intervention (2 PHCU)	Comparison (2 PHCU)	Total
Pregnant women	375	375	750

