Study Population	Main Data Collection Method	Other Study Procedures	Number of contacts	Duration of Research Interview (Only)	Place of Interview
	Review Client held Integrated MCH/Family Health Card (post intervention)				
Registers, Referrals at Health Center, Health post level	(Revised longitudinal register) For HEW monitoring tool: Ease of use, helpful for data review meetings, etc		12: monthly data review and abstraction	N/A	Health Post and Health Center

4. Provide a brief data analysis plan and a description of variables to be derived.

After data have been thoroughly examined for quality, the study team will perform exploratory data analysis of the key variables for checking frequency distributions, measures of variability, central tendency, and data outliers. We will also check for incomplete data and undertake an imputation strategy, if needed.

We will examine the differences in contraceptive use behavior by study arms for the following outcomes:

- Baseline only: % with past use of postpartum family planning among women with non-first pregnancies
- % of postpartum women who choose a method prior to delivery (by # of ANC contacts)
- % uptake of FP by PP timing (Delivery, PNC, immunization) and type of method
- % of ANC and PNC contacts where FP was discussed or provided (by type of contact, i.e., HDA, HEW, HCW, other)
- Duration of exclusive breastfeeding/Introduction of complementary foods
- % initiated LAM and the duration of LAM use
- % of women received counseling during immunization
- Immunization coverage of infants of enrolled women by month postpartum (doses of DPT1, 2 and 3 and drop out rates)

We will perform both “intent to analysis” to examine the net differences between the two study arms, adjusted for confounding covariates, and “per-protocol analysis” to examine “dose-effect” of health system contacts. We will fit multivariable logistic regression models for examining the differences in binary outcome variables (e.g., method selection during ANC; FP discussions during contacts, etc). We will use hazards regression model for examining the duration (discontinuation) of LAM use in first 6-month PP and for analyzing the uptake of modern contraceptive method by timing since delivery.

1. Describe whether you are collecting or storing personal identifiers, and if yes, why you need them, and when and how you plan to dispose of them. Signatures on consent forms are considered to be identifiers.

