#### A. Quantitative interviews with Women:

After data have been thoroughly examined for quality, the study team will perform exploratory data analysis of key variables such as checking frequency distributions, measures of variability, central tendency, and data outliers. We will also check for incomplete data and consider strategies to handle missing values such as undertaking an imputation strategy and weighting adjustments for non-responses.

We will compare differences by study arm for key variables. Analysis will account for clustering of variables at kebele (village) level using the Taylor linearization method. Differences between the arms for categorical variables will be assessed using the Pearson chi-squared test with the Rao-Scott correction. Differences in continuous variables will be assessed using an adjusted t-test. In case of substantial differences between the study arms, we will perform propensity score matching and perform the analysis with inverse probability weights.

Key descriptive variables:

- Sociodemographic data such as age, marital status, education, and socioeconomic status (nationally representative SES will be determined using the EquityTool described here: <http://www.equitytool.org/>)
- (Baseline only) Proportion of pregnant women with non-first pregnancies (non-primiparous) who previously used family planning
- Number of health system contacts where FP was discussed or provided, by type of contact (ANC, PNC, immunization, etc) and provider (facility provider, HEW, volunteer)
- Proportion of postpartum women who chose a method prior to delivery, by method, and received chosen method
- Proportion of postpartum women who used FP during the first 12 months after giving birth, by method
- Reasons for starting and stopping contraceptive methods and duration of use

- Initiation and duration of exclusive breastfeeding and lactational amenorrhea (LAM); average/median duration of postpartum amenorrhea, PP sexual initiation/PP abstinence
- Partner communication about family planning

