We will fit multivariable logistic regression models for the primary and secondary binary outcomes (see below) to examine differences between the study arms, adjusted for confounding covariates and clustering at kebele level. We will also conduct a “per-protocol analysis” by examining the “dose-effect” of health system contacts on the primary and secondary outcomes, regardless of study arm. We will run two dose-effect models, looking at the association between the outcomes and 1) the total number of contacts and 2) the number of contacts during which FP was discussed as reported by the woman. For the secondary outcome, we will only include contacts during pregnancy since contacts after the birth would not have a temporal effect on whether the woman chose a method prior to delivery.

- Primary outcome:
  - Proportion of interviewed postpartum women who used a modern family planning method within 12 months after giving birth
- Secondary outcome:
  - Proportion of interviewed postpartum women who chose a method prior to delivery

We will also conduct time-to-event analyses using life-table method and use a log-rank test to test for differences in survival distributions between the study arms in terms of the timing of FP uptake after birth. We will perform multivariable hazards model (Cox’s proportional model or parametric model with Weibull distribution in case of non-normality in hazards function) for adjusting confounding covariates and clustering effects.

Additionally, we will run hazards regression models for women who initiated exclusive breastfeeding/LAM after birth to test for differences between arms in the duration of exclusive breastfeeding/LAM use.

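### No censored-data method is assigned to duration of contraceptive use or of postpartum amenorrhea; under the SAP's default t-test, a comparison of method duration mixes when women start with how long they continue.

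*SAP*

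**What the plan says.** SAP section A (Quantitative interviews with Women) sets a general rule: "We will compare differences by study arm for key variables". Categorical variables get a Rao-Scott corrected chi-squared test. For the rest, "Differences in continuous variables will be assessed using an adjusted t-test". The list of key descriptive variables that follows includes "Reasons for starting and stopping contraceptive methods and duration of use" and "average/median duration of postpartum amenorrhea, PP sexual initiation/PP abstinence".

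Later in the same section, time-to-event methods are given to two things. A life table and log-rank test, with a Cox or Weibull model, are used to "test for differences in survival distributions between the study arms in terms of the timing of FP uptake after birth". Hazards regression among women who initiated exclusive breastfeeding/LAM is used "to test for differences between arms in the duration of exclusive breastfeeding/LAM use". The brief data analysis plan in Protocol section V is no wider: "We will use hazards regression model for examining the duration (discontinuation) of LAM use in first 6-month PP", plus uptake of a modern method by time since delivery.

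Neither document says how an episode still ongoing at interview enters the analysis. The missing-data text covers imputation and non-response weighting, which is a different problem.

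The interview time also varies. Protocol section III.B has women "interviewed at enrollment and at 12-month PP", while Table 5 in section V places the follow-up questionnaire at six to nine months postpartum.

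**The concern.** Both durations are right-censored at the follow-up interview: some women will still be using a method, and some will still be amenorrheic. The two variables then behave differently.

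For method use the clock starts when the woman starts the method, so the longest duration that can be observed is the interview time minus the start time. The intervention promotes family planning from pregnancy onward, and the SAP itself tests whether uptake timing differs by arm. If uptake does come earlier, intervention users have a longer window. Their mean observed duration then rises even when they stop at the same rate, and a reader could take this as better continuation.

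For amenorrhea the clock starts at birth in both arms, so the start-time mechanism does not apply. Truncation at interview still shortens the means.

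**Working it through.** **The plan's own figure.** The documents give no figure for either duration. The only related number is the sample size for uptake (Protocol section III.B). The stated formula with 20% vs 10%, two-sided 0.05 and 80% power gives 198.96; × 1.5 = 298.4, rounded up to 299, as stated. Nothing below depends on it.

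**Inputs.** The 12-month interview is from Protocol section III.B. Start months, stopping hazards and median amenorrhea are not in the documents, so all are assumptions.

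**Method use, ongoing episodes cut at interview.** With constant monthly hazard h and window w = 12 − start month, mean observed duration is (1 − e^(−hw))/h.

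Intervention start at month 2 (w = 10), h = 0.05: (1 − e^(−0.5))/0.05 = 7.87 months. Comparison arm, also h = 0.05:

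| Comparison start | w | Mean (months) | False gain |
|---|---|---|---|
| month 3 | 9 | 7.25 | 0.62 |
| month 4 | 8 | 6.59 | 1.28 |
| month 5 | 7 | 5.91 | 1.96 |
| month 6 | 6 | 5.18 | 2.69 |

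Now double the intervention hazard to 0.10: (1 − e^(−1))/0.10 = 6.32. Against the same comparison means, the order is correct at months 3 and 4 (6.32 vs 7.25 and 6.59) and reversed at months 5 and 6 (6.32 vs 5.91 and 5.18). The means are equal when (1 − e^(−0.05w))/0.05 = 6.32, so w = 7.60 and the start gap is 10 − 7.60 = 2.4 months. At the four-month gap, the intervention hazard must reach about 0.15 before the means meet: (1 − e^(−1.5))/0.15 = 5.18.

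The threshold depends on the hazards. If 60% vs 75% are still using 12 months after starting (earlier vs later arm), the means are about equal at a one-month gap (8.14 vs 8.10) and reversed at three months (8.14 vs 6.44).

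**Method use, ongoing episodes dropped.** The mean of completed episodes is [(1 − e^(−hw))/h − w·e^(−hw)]/(1 − e^(−hw)). With h = 0.05 in both arms, w = 10 gives 4.59 and w = 6 gives 2.85, a false gain of 1.7 months. Dropping ongoing users does not remove the problem.

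**What the tests would do.** In 4,000 simulated trials per case, with clustering ignored, users numbered 60 and 30 (20% and 10% of 299) and starts were near months 2 and 5. Ongoing episodes were cut at interview for the t-test and censored for the log-rank test.
- Equal 70% twelve-month continuation: the t-test significantly favoured the earlier starters in 99.5% of trials. The log-rank test rejected in about 5%, both directions together.
- 60% (earlier arm) vs 75%: the t-test significantly favoured the arm with worse continuation in 91%. The log-rank test did so in under 0.1% and correctly found that arm worse in 16%.

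**Amenorrhea.** Assume exponential durations with medians of 8 and 9 months, so the full means are 8/ln 2 = 11.54 and 9/ln 2 = 12.98, a difference of 1.44. Cut at a common 12-month interview, they become 7.46 and 7.83, a difference of 0.37 in the right order, with 35% and 40% still ongoing. Only if the first arm were interviewed at 12 months and the second at 9 would the order reverse (7.46 vs 6.49).

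**The case against.** The strongest reply is that the t-test sentence is a generic rule and these are descriptive items. Being on the list does not settle the method: exclusive breastfeeding/LAM duration shares a bullet with amenorrhea, yet it receives hazards models. The authors plainly recognise time-to-event data, and a median for amenorrhea could come from a life table. This softens the point but does not remove it. The exception for LAM is written down and none is written for the other two durations, so an analyst following the text arrives at the t-test.

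Three stronger readings are tempting, and the documents do not support them.
- A reader might infer that ongoing episodes are coded as stopped at interview. The SAP does not say so. The gap is a missing rule, and dropping ongoing episodes is also biased.
- A reader might infer that the arm with worse continuation will generally look better. Under 10% vs 5% hazards that needs a start gap above about 2.4 months, and the documents give no start times. What appears with any earlier start, at equal stopping, is a false gain.
- A reader might extend the reversal to amenorrhea. All women share birth as the origin, and no passage says that interview timing differs by arm.

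It is also fair to say that uptake timing is analysed separately, so a shift in start time would be visible, and that the plan announces no claim about continuation.

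**Conclusion.** The concern holds for duration of method use. The stated rule gives a biased comparison whenever start times differ between arms. With a 12-month interview, equal 5% monthly stopping and an intervention start at month 2, the false gain runs from about 0.6 months (one-month gap) to 2.7 months (four-month gap) when ongoing episodes are cut at interview. These sizes rest on assumed start months and constant hazards.

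For amenorrhea the consequence is milder: shortened means and a diluted difference, with the order kept under proportional hazards and equal interview timing. The conflict between 12 months and six to nine months leaves that timing unsettled, but it is not evidence of a difference between arms.

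Neither duration is a primary or secondary outcome. The uptake analysis, the choice-before-delivery analysis and the 299 per arm are unaffected. The change should be made, but the main result does not depend on it.

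**What to change.** In SAP section A:

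1. Limit the adjusted t-test to continuous variables that are fully observed for every woman.
2. Analyse duration of method use from method start to stopping, and amenorrhea from birth to return of menses. Use a life table and a hazards model with clustering at kebele level, and censor ongoing episodes at the interview date.
3. Report life-table estimates in place of raw means. A median may not be reached for method use; the proportion still using at a fixed time since start would then serve. A breakdown by method is optional, because the planning rates imply only about 60 and 30 users (20% and 10% of 299).
4. Reconcile the follow-up interview time between Protocol section III.B and Table 5, and record each woman's interview date relative to birth.

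The cost is a few sentences and a small amount of analysis, since the life-table and hazards methods are already planned for other outcomes. The SAP lists duration and reasons for stopping but does not mention stop dates, so the sponsor should confirm that the questionnaire captures start and stop timing and whether each episode is ongoing.

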The Ethiopian health system envisages that a number of health contacts should occur for women and babies from pregnancy through to the extended postpartum. Figure 1 below illustrates these contacts.

Figure 1: Possible Contacts with the Health System for Pregnant Women in Ethiopia

Month	4	5	6	7	8	9		1	2	3	4	5	6
Client	Pregnancy						Birth	Postpartum Period					
HDA	x	x	x	x	x	X	Home	X	x	x	x	x	x
HEW	Quarterly visits: 2-3 times during last two trimesters of pregnancy							Quarterly visits: 2-3 times during first 12 months postpartum					
HC	ANC1 Before end of 4 th month		ANC2 24-28 weeks	ANC3 32 weeks	ANC4 36 weeks	Facility		PNC w/in 48 hours; w/in 6 weeks					
								DPT1 6 weeks		DPT2 10-14 weeks		DPT3 14-22 weeks	

About 84% infants receive at least one dose and more than 60% receive two doses of basic vaccines. A substantial number of mothers also seek care for their child's fever, diarrhea and other illness from health providers. This study will take these contact occasions as opportunities for promoting PFP, but also to reinforce the need to fully vaccinate children.

III. Study Design

- A. Provide an overview of your study design and methods. The study design must relate to your stated aims/objectives. Details will be requested later. If your study also involves analysis of existing data, please complete Section XI, "Secondary Data Analysis of Existing Data" in the last part of this research plan. If your study ONLY involves analysis of existing data, please use the research plan template for secondary data analysis (JHSPH IRB Research Plan for Secondary Data Analysis of Existing Data/Specimens).

This implementation research will use a quasi-experimental mixed method design with two arms. The intervention arm will have integrated PFP messages at each level of health system contacts. The control arm will continue to deliver the existing FP services at primary health care centers only.

The primary study population is a cohort of pregnant women, enrolled between the 2nd and 3rd trimester of pregnancy in both arms, who will be followed to twelve months post-partum. We will interview the women at study enrollment and at the end of the study. We will track women's contacts with the health system, particularly regarding PFP counseling, decision making and contraceptive adoption, through chart reviews of routinely collected facility and community based health records and registers (e.g. family folders that may be modified for study).

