Prior to study implementation, we will conduct a readiness assessment of selected health facilities in both study arms to ensure that the supplies, equipment and commodities are available for PFP counseling and service delivery capacity in all health centers. Gaps in PFP service delivery will be addressed in both intervention and control study sites. Health center maternity staff will be trained in PFP (PFP counseling, postpartum IUD and implant provision, etc.) in accordance with current Government of Ethiopia PFP expansion strategies. The rapid assessment will provide an understanding of service delivery capacity and needs and allow MCSP to ensure the same services and equipment are available in all sites.

[figure not shown]
In intervention sites, both facility-based providers at primary health center and health post levels, including HEW and HDAs, will receive training on PFP counseling and use of adapted health records. Should HEW require refresher training in implant provision or other methods, the study will also provide this.

In addition, we will conduct a rapid formative assessment to understand the health system and cultural contexts of PFP needs during the preparatory phase of intervention implementation. This formative study will include household members of pregnant women, community health workers (HDAs), and facility-based providers, including HEWs, and managers. This rapid assessment will support the design of the intervention at the community level which will include designing and training HEWs to communicate PFP messages as part of a bundle of messages that promotes high impact maternal, newborn, and child health (MNCH) practices and care-seeking behavior. HEWs at health posts in the intervention site only will receive additional training on tracking clients and providing PFP messaging (as well as other FP/implant refresher as needed) at routine antenatal and postpartum contacts. HEWs in the intervention site will train HDAs on these messages and will receive job aids and tracking tools for PFP messaging. Data from chart reviews and review of health records in the intervention and control arms will be analyzed to determine differences in PFP counselling, decision-making on method choice, and uptake of PFP by study arm.

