## Analysis Plan

### Utilizing All Health System Contacts to Offer Postpartum Family Planning (PPFP) to Pregnant Women and Women within Twelve Months Postpartum in Ethiopia

This plan describes how data collected through different methods will be analyzed after cleaning in order to meet these research objectives:

1. Estimate the added effect of the community-based intervention by comparing uptake of PPFP through 12 months postpartum in intervention and comparison sites (“intent to treat” analysis)
2. Assess the effect of systematically integrating PPFP messages into contacts with the health system on uptake of PPFP through 12 months postpartum using a dose-response analysis based on the number of contacts (“per protocol” analysis)
3. Explore the feasibility of tracking PPFP and reviewing data at health centers and HEWs and volunteers using record keeping and review processes to track women's decision-making and contraceptive use from pregnancy through 12 months postpartum
4. Explore factors influencing women's/couples' adoption of PPFP during the first 12 months postpartum

Quantitative and qualitative data analysis will be triangulated to help interpret results and provide deeper insights on study objectives.

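### The dose-effect models pool both arms with no stated arm term, so the slope for FP-discussed contacts mixes the arm difference with the within-arm association

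*SAP*

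**What the plan says.** SAP section A sets out two kinds of model for the primary outcome (modern method use within 12 months of birth) and the secondary outcome (method chosen before delivery).

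- **Arm comparison.** Multivariable logistic models "to examine differences between the study arms, adjusted for confounding covariates and clustering at kebele level".
- **Dose-effect (per-protocol) analysis.** Run "on the primary and secondary outcomes, regardless of study arm", as two models with different exposures: "1) the total number of contacts and 2) the number of contacts during which FP was discussed as reported by the woman". No arm, PHCU or woreda term, stratification or interaction is named. The adjustment wording of the arm comparison is not repeated.

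SAP section C adds that stock-out data and counseling quality will be used in the per-protocol analyses, but not how. SAP objective 2 gives the purpose: "Assess the effect of systematically integrating PPFP messages into contacts with the health system on uptake of PPFP through 12 months postpartum". Protocol aim 1b likewise asks for the effect of each further contact.

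Protocol section III.A describes how the arms differ. "The intervention arm will have integrated PFP messages at each level of health system contacts", whereas "The control arm will continue to deliver the existing FP services at primary health care centers only". It adds: "HEWs at health posts in the intervention site only will receive additional training on tracking clients and providing PFP messaging". Refresher training in implants or other methods where needed, job aids and tracking tools are also described for the intervention sites.

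**The concern.** Arm is built to change the exposure in the second dose model, because family planning should be discussed at more contacts in the intervention arm. Arm can also change uptake by routes that leave the count alone: client tracking, implant skills, job aids, and any pre-existing difference between the few PHCUs in each arm. A variable that moves both exposure and outcome confounds the slope when it is left out.

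Objective 2 is listed separately from objective 1 and worded as an effect of contacts. If the slope partly restates the arm difference, it is not separate evidence that more contacts lead to more uptake. A reader of the results could not tell how much of it is the arm difference.

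**Working it through.** **1. The plan's own figure.** From protocol section III.B: p1 = 0.20, p2 = 0.10, two-sided alpha 0.05, power 80%, design effect 1.5.

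n = {1.960 × √(2 × 0.15 × 0.85) + 0.8416 × √(0.16 + 0.09)}² / 0.10² = (0.9897 + 0.4208)² / 0.01 = 198.96

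198.96 × 1.5 = 298.4, so 299 per arm, as stated. No figure is given for the dose-effect models.

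**2. Worst-case truth.** Uptake is 20% vs 10%, and contacts have no effect within either arm, so the whole difference bypasses the count. The documents give no contact means or distributions, so these are assumptions: means of 3, 4 or 6 vs 2 FP-discussed contacts, with Poisson counts or overdispersed counts (gamma-Poisson, shape 2).

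**3. Hand check, 4 vs 2, Poisson.** On the linear scale the pooled slope is the between-arm slope times the between-arm share of the variance in contacts.

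- Between-arm slope: (0.20 − 0.10) / (4 − 2) = 0.05 per contact
- Between-arm variance: ((4 − 2)/2)² = 1; mean within-arm variance: (4 + 2)/2 = 3; share: 1/4
- Pooled slope: 0.05 × 1/4 = 0.0125; on the logit scale 0.0125 / (0.15 × 0.85) = 0.098, odds ratio about 1.10

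With overdispersion the within-arm variance is m + m²/2, that is 12 and 4, mean 8. The share falls to 1/9, and 0.05 / 9 / 0.1275 = 0.044, odds ratio about 1.04.

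**4. Logistic fit.** The population logistic slope was computed by weighted maximum likelihood. Its standard error was scaled to 299 per arm with design effect 1.5, an effective 598 / 1.5 = 399 women. The probability of significance is P(|Z + slope/SE| > 1.96). For 4 vs 2 Poisson, 0.0939 / 0.0674 = 1.39, giving 29%.

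| Mean FP-discussed contacts | Poisson: OR per contact | Poisson: falsely significant | Overdispersed: OR | Overdispersed: falsely significant |
|---|---|---|---|---|
| 3 vs 2 | 1.07 | 13% | 1.03 | 9% |
| 4 vs 2 | 1.10 | 29% | 1.04 | 15% |
| 6 vs 2 | 1.10 | 50% | 1.04 | 26% |

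With arm in the model the odds ratio is 1.00 in every row. In separate simulations with other means (3 to 8 vs 3 FP-discussed contacts, 11 to 14 vs 10 total contacts), the arm term brought the false-positive rate back to about 5%.

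**5. Milder truth.** In the approximation of step 3 the false part shrinks in proportion to the share of the arm difference that bypasses contacts. If half bypasses them, at 4 vs 2 Poisson, it is 0.025 × 1/4 / 0.1275 = 0.049, an odds ratio near 1.05 instead of 1.10.

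**6. Total contacts.** With equal means (10 vs 10) the pooled odds ratio is 1.00 and the rejection rate 5%. At 11 vs 10 (Poisson) they are 1.02 and 7%.

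**The case against.** - **The phrase may only say who is included.** It can mean women of both arms, analysed by contacts received. It does not exclude an arm covariate, and the sentence before it plans adjusted models. This stands as far as it goes: a reader might infer that the SAP rules out adjustment for arm, and it does not. It names no arm term, however, and pooling is the natural reading.
- **Between-arm variation is partly real dose.** The intervention consists largely of messages placed in contacts. If its effect runs through them, the pooled slope is not false. This stands, and it makes the table a worst case. The pooled model still cannot separate the two routes.
- **Counseling quality and stock-outs are already to be used.** This is a partial answer. The SAP does not say how they enter, and supervision covers all study health centers but only intervention health posts.
- **Poisson counts flatter the result.** This stands. Overdispersion is plausible for visit counts, and the assumed form roughly halves the rejection rates.
- **A reader might infer that both dose models are biased.** The documents do not support this for total contacts. Messages are largely added to contacts that already exist, so totals may hardly differ by arm. A separate issue remains: a community contact carries the trained messages only in the intervention arm, so one slope averages two different exposures.
- **Conditioning on arm or PHCU has its own cost.** This stands. It removes variation created by random assignment of PHCUs and leaves women's own care-seeking, which may drive both contacts and uptake.

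**Conclusion.** The point holds for the model of FP-discussed contacts. As written, its slope combines the arm contrast with the within-arm association and cannot on its own answer objective 2 separately from objective 1. At worst the false odds ratio per contact is 1.07 to 1.10, with 13% to 50% false significance (Poisson), or 1.03 to 1.04 with 9% to 26% (overdispersed).

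These sizes rest on assumed contact means and distributions, and on the whole 20% vs 10% difference bypassing contacts. The upward direction needs only more such contacts in the intervention arm and some higher uptake there by other routes.

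For total contacts the bias needs a difference in totals that the documents do not establish; the point there is the different content of a contact by arm. A reader might also infer that the primary result is in doubt. It is not, because the arm comparison is a separate model.

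**What to change.** In SAP section A, state that:

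1. the dose-effect models include women of both arms, with study arm and woreda as covariates;
2. they carry the same confounder and kebele-cluster adjustment as the arm comparison;
3. the slope is reported within each arm together with the arm-by-contacts interaction, chiefly for total contacts;
4. the unadjusted pooled slope may be shown alongside, labelled as including the between-arm difference.

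Arm and woreda are preferable to a fixed set of PHCU indicators, because protocol section III.B allows enrollment from adjoining kebeles in non-study PHCUs and the number of PHCUs is therefore not settled.

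The cost is a few sentences and model terms, with no new data. Some precision is lost, because contact variation produced by the arm no longer informs the slope. The within-arm slope also remains an observational association open to confounding by women's own care-seeking, and should be reported as such.
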